**LIST OF ABBREVIATIONS**

AE	Adverse Event
CFR	Code of Federal Regulations
CMP	Clinical Monitoring Plan
CRF	Case Report Form
CRO	Contract Research Organization
DISCSS™	Dynamic Interferential Spinal Cord Stimulation System
eCRF	Electronic Case Report Form
EPG	External Pulse Generator
FDA	Food and Drug Administration
GCP	Good Clinical Practice
HIPAA	Health Insurance Portability and Accountability Act
ICH E6	International Conference on Harmonization Guidance for Industry, Good Clinical Practice: Consolidated Guidance
IDE	Investigational Device Exemption
IFC	Interferential Current
IFT	Interferential stimulation therapy
IRB	Institutional Review Board
ISO	International Organization for Standardization
NRS	Numeric Rating Scale
OHRP	Office for Human Research Protections
PI	Principal Investigator
SAE	Serious Adverse Event
SCS	Spinal Cord Stimulation
SOP	Standard Operating Procedure

## 1.0 INTRODUCTION

Chronic pain affects up to 20% of the population in developed nations. This represents a profound impact on individuals and their families as well as a burden on employers and health care providers. The management for non-cancer related chronic pain varies. The current standard of care is multidisciplinary and includes pharmacological, psychological and physical therapies, as well as surgical interventions. Opioid analgesics are often prescribed, despite long-term contraindications. For many patients the current multidisciplinary approach has not been effective or results in undesirable side effects. Neuromodulation techniques may be an option for those individuals who have not benefited from other chronic pain interventions.

The Meagan Medical, Inc., Dynamic Interferential Spinal Cord Stimulation System (DISCSS™) System is used to deliver spinal cord stimulation (SCS) via interferential stimulation therapy (IFT) for the purpose of providing pain relief. The DISCSS™ system is intended for use in an investigational device exemption (IDE) study to assess the efficacy of interferential spinal cord stimulation for treating chronic back pain.

The mechanism of action for SCS was first proposed by Melzack and Wall in 1965. [name] published the first report of electrical stimulation of the spinal cord in 1967. Patients in whom SCS has been commonly applied are those with chronic back and leg pain and failed back surgery syndrome. In 2010, Nevro entered the SCS market with high frequency stimulation at 10,000 pulses per second, and their studies in pain patients have demonstrated superior back pain relief with a less uncomfortable stimulation sensation than traditional low-frequency SCS. Meagan Medical has designed and developed a trial stimulator using interferential current (IFC) stimulation. IFC stimulation is a type of electrical stimulation that uses paired electrodes with two independent circuits carrying high-frequency and medium-frequency alternating currents. It is believed that IFC stimulation permeates the tissues more effectively and with less unwanted stimulation of cutaneous nerves. Meagan Medical calls their system the “Dynamic Interferential Spinal Cord Stimulation System” (DISCSS™).

The DISCSS™ device utilizes two intersecting circuits of medium frequency sine waves that are in the range of 500-20,000 Hz. The higher base frequencies reduce tissue reactance and the intersection of the two circuits produce a steerable “sweet spot” of stimulation that has a resultant beat frequency. Due to these two advantages, the DISCSS™ is anticipated to result in more effective pain relief than other commercially available SCS systems. This pilot feasibility study will explore and help determine optimal settings and configuration of the DISCSS™ System with patients that have completed a percutaneous trial with a commercially available SCS trial system.

## 2.0 STUDY OBJECTIVES

### 2.1 Primary Objectives

- Effectiveness: To assess the performance of the DISCSS™ device in achieving back pain reduction as compared to baseline by patient report using a Numeric Rating Scale (NRS) and Anatomical Pain Maps in a cohort of patients with chronic back pain during a three -four day trial of the SCS DISCSS™ system.
- Safety: To evaluate the safety of the DISCSS™ device by reviewing adverse events and serious adverse events in trial participants.

### 2.2 Secondary Objective

- To describe patients' experience and perceptions with the use of the DISCSS™ device for management of chronic back pain through analysis of their responses to a subjective evaluation questionnaire.

## 3.0 STUDY DESIGN

### 3.1 Description of Study Design

This investigation will be performed as a prospective, multicenter, open-label feasibility study. Thirty (30) patients with back pain greater than leg pain who were candidates for Spinal Cord Stimulation (SCS) and have successfully completed a percutaneous trial with a commercially available SCS system will be trialed with a 3-4 day exposure to the investigational DISCSS™ device. The trial will be conducted at 5-7 U.S. centers. The percutaneous trial leads from the commercial system will be connected to the External Pulse Generator of the DISCSS™ Trial System and the patients will be trialed for an additional three-four days.

The investigational product for this feasibility trial will be the DISCSS™ system, not the commercially available trial SCS system. Exposure to the commercially available trial SCS system will be considered background therapy. The purpose of the background therapy phase is to establish baseline pain levels and determine patients' eligibility to continue to the investigational phase of the trial using the DISCSS™ SCS phase of the trial. Pain assessment and complications data from the commercial spinal stimulation system will be collected during the background therapy phase. The pain and complications data from the background therapy phase will not be analyzed in terms of the study endpoints.

Commercial device selection will be left to the discretion of the Investigator. Some of the frequently used commercially available trial SCS systems include Prodigy Neurostimulation System (St. Jude Medical (ABBOTT)), Medtronic SCS, the Senza System (Nevro Corporation), and the Precision Plus (Boston

Scientific). The Sponsor will not be responsible for the cost or complications that occur during the use of the commercial trial system.

### **3.2 Primary Endpoints**

The primary effectiveness endpoints for this study will include:

- Pain intensity ratings on a Numeric Rating Scale (NRS); and
- Anatomical Pain Maps demonstrating location of Back Pain, Leg Pain and Overall Pain

The primary safety endpoints for this study will include:

- Incidence of adverse events arising from the DISCSS™ treatment phase
- Incidence of serious adverse events arising from the DISCSS™ treatment phase

### **3.3 Secondary Endpoints**

The secondary endpoint for this study will include:

- Patient descriptions of device efficacy and device stimulation sensation as captured on a study-specific questionnaire

## **4.0 STUDY ENROLLMENT AND WITHDRAWAL**

### **4.1 Inclusion Criteria**

In order to be eligible to participate in this study, an individual must meet all of the following criteria:

- a) Age greater than 21 years and less than 80 years
- b) Has a diagnosis of chronic neuropathic pain of trunk and limbs
- c) Is eligible for a spinal cord stimulation trial of a commercially available SCS trial system. Subjects will be evaluated at the end of the background Commercial SCS Device phase for complications and appropriateness to continue to the investigational phase with the DISCSS™ system. Complications from the background phase with the commercial SCS device may include, but are not limited to unusual pain or discomfort during the trial stimulation, local skin reactions or infection at the implant site.
- d) Has a Back Pain Score of minimum intensity 5.0 on a Numeric Rating Scale (NRS)
- e) Has an NRS Back Pain Score that is greater than both Leg Pain Scores
- f) Is not a candidate for revision surgery
- g) Has completed a minimum of 6 weeks of conservative therapy (physical therapy, anti-inflammatory medications, or similar therapies) with limited or no reduction in back pain
- h) Is willing to adhere to the warnings associated with the DISCSS™ system

- i) Is willing to halt and/or modify the use of all prescription and over-the-counter analgesics per the Investigator's direction during study participation
- j) Is capable of providing written informed consent
- k) Is able to comply with the requirements of study visits, follow-up phone visits and self-assessment questionnaires
- l) If existing permanent implanted leads are in place, the patient must be undergoing a paradigm shift in treatment (e.g. Conventional Sensory SCS to Sub-Perception SCS) that necessitates trialing of the new commercial SCS device.

#### **4.2 Exclusion Criteria**

An individual who meets any of the following exclusion criteria at screening will be excluded from participation:

- a) Is a poor surgical candidate by determination of the Investigator
- b) Is unable to operate or understand the use of the commercial or investigational Spinal Cord Stimulator systems
- c) Has an active systemic infection
- d) Has exposure to shortwave, microwave or ultrasound diathermy at home or at work
- e) Has occupational exposure to high levels of non-ionizing radiation such as radio or cell phone transmission stations, facilities using radiofrequency heat sealers or induction heaters, or electric power infrastructure controlled environments
- f) Has an implanted cardiac system (e.g. pacemakers)
- g) Is currently participating in another clinical study
- h) Is currently pregnant or lactating, or not using adequate birth control
- i) Has any untreated major psychiatric comorbidity
- j) Has serious drug-related behavioral issues per Investigator's assessment
- k) Has a bleeding complication or coagulopathy
- l) Requires concurrent use of anticoagulant therapy such as heparin, warfarin, rivaroxaban, dabigatran, apixaban, edoxaban, enoxaparin, fondaparinux
- m) Is immunocompromised and at risk for infection
- n) Has insulin-dependent diabetes not controlled through diet and/or medication
- o) Has chronic pain related to malignancy
- p) Has used a commercially available SCS device within the last 14 days
- q) Is otherwise determined, based on the opinion of the Investigator to be an unsuitable candidate for this study

#### **4.3 Early Discontinuation**

The participant may withdraw participation in the trial for any reason. Possible reasons for early discontinuation by the participant include:

- Consent withdrawal
- Inability to tolerate the background SCS trial phase with the commercially approved device
- Occurrence of a clinical adverse event or development of a medical condition such that continued participation in the study would not be in the best interest of the participant

The Investigator may also discontinue a patient from the study in the event of:

- The participant meets an exclusion criterion (either newly developed or not previously recognized) that precludes further study participation
- Any medical event/condition that presents a health or safety risk and prevents the participant from continuing in the study
- Participant's failure to comply with protocol requirements
- Administrative reasons (e.g. Sponsor's decision to stop the study)
- Device complication

At the time of early discontinuation, the SCS device will be removed.

Percutaneous trial leads will be removed, if applicable. All end of study evaluations will be completed, and study completion source documents and case report forms will be completed. All adverse events will be followed by the Investigator until resolution.

#### **4.4 Missed Visits**

Contact information for the participant and an alternate contact (i.e. a friend, relative, etc.) will be collected at Visit 1 and documented in the records. Any participant who misses one scheduled appointment will be contacted the same day by study site personnel. Telephone contact will be repeated at least daily for 3 days. A certified letter (or its equivalent) will be sent to the participant's last known address. All attempts will be made to arrange an appointment to remove the device and leads as well as collect any end of study evaluations, as applicable. Participants who are determined to be lost to follow up after 3 phone contacts and a certified letter cannot be considered for re-enrollment.

#### **4.5 Use of Data from Early Discontinuation Cases**

Study data collected previously for patients who are discontinued from the study by the Investigator or lost to follow-up may still be included and used for the study unless the patient presents written notification of withdrawal of consent to the Investigator. In the event that a patient withdraws consent to participate in the study, data previously collected for the patient may not be included or used for the study.

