## **8.9     Device Complications**

In the event of a device malfunction or complication, subjects will be advised to return to the clinic for evaluation as described in Section 6.7 Unscheduled Visits. The device complications and/or adverse events will be addressed clinically and per the procedures outlined in the protocol Study Procedures Section 6.0, Safety Reporting Section 10.0 and the DISCSS™ Stimulator System Clinician Use Guide. If indicated, the Investigator will adjust the settings on the DISCSS™ Stimulator System or, if necessary replace the DISCSS™ Stimulator System according to the Clinician Use Guide as outlined in Section 8.9. If the complication cannot be resolved, the subject will be discontinued from the study as described in Section 4.6.

All information regarding the adverse event, device malfunction or complication and replacement, as applicable will be captured in the medical records, Case Report Forms and entered into the clinical database. The malfunctioning device will be returned to Meagan Medical where the device use logs will be downloaded and analyzed.

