## **10.0    SAFETY REPORTING**

### **10.1    Overview and Definitions**

All adverse events associated with the DISCSS™ will be recorded and analyzed. Regulations contained in the FDA and ICH Guidelines will be followed in the identification, reporting and analysis of adverse events.

**Adverse Event:** An adverse event (AE) is any untoward medical occurrence, disease, injury, or untoward clinical signs (including abnormal laboratory findings, surgical complications, etc.), whether related or unrelated to the investigational device or its use.

**Anticipated Adverse Device Effect:** Any adverse effect related to the device, which is identified in the protocol prior to study commencement.

**Serious Adverse Event (SAE):** A Serious Adverse Event is an adverse event which:

- Led to a death,
- Resulted in life threatening illness or injury\*
- Resulted in patient hospitalization or prolongation of existing hospitalization,
- Resulted in patient disability or permanent damage or required intervention to prevent permanent impairment/damage
- Led to a congenital abnormality or birth defect

\* NOTE: the term “life-threatening” refers to an event in which the patient was at a risk of death at the time of the event; it does not refer to an event which hypothetically might have caused death if it were more severe.

**Unanticipated Adverse Device Effects (UADE):** An Unanticipated Adverse Device Effect is:

1. Any serious adverse effect on health or safety or any life threatening problem or death caused by, or associated with, a device, if that effect, problem, or death is not identified in nature, severity, or degree of incidence in this protocol; or
2. Any other unanticipated serious problem associated with a device that relates to the rights, safety, or welfare of the patients.

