## 10.2 Safety Monitoring

The Sponsor/designee will monitor all adverse event reports to identify and trend all events that would require temporary discontinuation of study enrollment, to fully characterize device safety, to modify the study protocol, or to terminate the study.

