## **10.7 Determination and Reporting of Unanticipated Adverse Device Effects**

The Sponsor shall review all reported SAEs to evaluate whether they meet the criteria for an Unanticipated Adverse Device Effect. For adverse events that are determined to be UADEs, the Sponsor will submit an expedited safety report to the FDA's Center for Devices and Radiological Health (CDRH). The expedited safety report will consist of a completed Form FDA 3500A and a cover letter analyzing the significance of the event. The expedited safety report will be submitted to the FDA as soon as possible and, in no event, later than 10 working days after the Sponsor first receives notice of the UADE. A copy of this safety report will be provided to all participating study Investigators.

If, following receipt and investigation of follow-up information regarding an adverse event that was previously determined not to be a UADE, the Sponsor determines that the event does meet the requirements for expedited reporting, the Sponsor will submit a completed Form FDA 3500A and cover letter as soon as possible, but in no event later than 10 working days after this is determined.

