## **12.0 STATISTICAL CONSIDERATIONS**

For this feasibility study, descriptive statistics will be utilized to describe the data for each endpoint. For continuous variables, this include the mean value, change from baseline, standard deviation, and 95% confidence interval. For categorical variables, the rate and a 95% confidence interval will be presented. As there is no comparator group for this clinical study, no hypothesis-based statistical testing is planned. For adverse event information, the

number of events, the number of subjects experiencing events, and the rate of subjects experiencing an event will be presented.

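### Section 4.5 bars all data from patients who withdraw consent, adverse events included, although section 10.1 promises that every DISCSS-associated event will be analyzed

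*Protocol*

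**What the plan says.** Protocol section 4.5 has two rules on data from patients who leave early.

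- Patients discontinued by the investigator or lost to follow-up: data already collected may still be used, "unless the patient presents written notification of withdrawal of consent to the Investigator".
- Patients who withdraw consent: "data previously collected for the patient may not be included or used for the study".

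Neither rule sets safety data apart. In isolation, the auxiliary in the second rule could mean either a possibility or a ban. The preceding sentence permits use subject to an exception, so the second rule reads as a ban.

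Section 10.1 makes an unqualified commitment: "All adverse events associated with the DISCSS™ will be recorded and analyzed". Section 3.2 makes adverse event incidence in the DISCSS phase a primary safety endpoint, together with "Incidence of serious adverse events arising from the DISCSS™ treatment phase". Section 12.0 reports the number of events and the number of subjects with events, and says that "the rate of subjects experiencing an event will be presented". It does not name the denominator of that rate.

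**The concern.** Take a patient who has an adverse event on DISCSS and then withdraws consent. Section 10.1 requires the event to be analyzed. Section 4.5 forbids its use. An analyst cannot follow both, and no other section gives one priority. A statistical analysis plan could not settle this on its own, because keeping the event would breach 4.5 and dropping it would breach 10.1.

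The primary safety result is at stake. The study has one arm and 30 patients, so each patient is worth 1/30 = 3.3 percentage points. With no comparator and no hypothesis test, the counts are themselves the finding. The loss also need not be random: section 4.3 lists withdrawal of consent and the occurrence of an adverse event together as reasons for a participant to leave, and one may lead to the other. Removing known events from the primary count also works against the aim in section 10.2 "to fully characterize device safety".

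**Working it through.** **Step 1: where the passages conflict.** The conflict concerns analysis, not recording.

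| Section | What it governs | Effect on an event in a patient who withdraws consent |
|---|---|---|
| 4.5 | use of data | excluded from the study's data |
| 10.1 | recording and analysis | must be analyzed |
| 10.3 | recording | recorded on the case report form |
| 10.2, 10.7 | sponsor monitoring and review of serious events | still reviewed |
| 3.2, 12.0 | primary safety incidence | missing if 4.5 is followed |

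Sections 4.3, 6.8 and 10.3 cover collection, follow-up and recording, and do not directly contradict 4.5. They do leave open whether data gathered on the day of withdrawal, or in later follow-up of an event, may be used.

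The two rules in 4.5 also differ in their trigger: the first requires written notice of withdrawal, the second does not.

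**Step 2: possible effect on the primary rate.** The protocol states no figure to reproduce.

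Inputs:
- N = 30 (section 3.1).
- Event counts, withdrawal counts and the denominator are assumptions, because the protocol gives none of them.
- The interval type is also an assumption. Exact (Clopper-Pearson) 95% limits are used. For x subjects with an event out of n, the lower limit is the 0.025 quantile of Beta(x, n − x + 1) and the upper limit is the 0.975 quantile of Beta(x + 1, n − x).
- For x = 0 the lower limit is 0 and the upper limit is 1 − 0.025^(1/n). This gives 11.9% for n = 29 and 11.6% for n = 30.

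| Assumed case | All data kept | Data removed, patient out of denominator | Data removed, patient left in denominator |
|---|---|---|---|
| One patient with a serious event, who withdraws consent | 1/30 = 3.3% (0.1–17.2%) | 0/29 = 0% (0–11.9%) | 0/30 = 0% (0–11.6%) |
| Three patients with an adverse event, one of whom withdraws consent | 3/30 = 10.0% (2.1–26.5%) | 2/29 = 6.9% (0.8–22.8%) | 2/30 = 6.7% (0.8–22.1%) |
| Three patients with an adverse event; a different, event-free patient withdraws consent | 3/30 = 10.0% (2.1–26.5%) | 3/29 = 10.3% (2.2–27.4%) | 3/30, unchanged |

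**Step 3: direction.** If the withdrawn patient also leaves the denominator, the rate can move either way (rows 2 and 3), and it is biased only if withdrawal of consent is related to the outcome. If the patient stays in the denominator with the data removed, the rate can only fall or stay the same. In either case the event disappears from the count. The intervals overlap widely, so the table shows what can be lost, not a bias that will occur.

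**The case against.** The strongest reply is that the sections can be read together. Section 10.1 is a general statement under an overview heading and 4.5 is the specific rule, so 10.1 could be taken to cover only usable data. The word analyzed might also be satisfied by the sponsor's monitoring in 10.2 and by 10.7, where "The Sponsor shall review all reported SAEs to evaluate whether they meet the criteria for an Unanticipated Adverse Device Effect". Section 4.5 does not stop that review or expedited reporting. This reading is possible, but it does not rescue the endpoint: sponsor review does not return the event to the incidence in sections 3.2 and 12.0.

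The second reply is that the route is narrow, and this largely stands. DISCSS exposure lasts 3–4 days. Section 4.3 lists consent withdrawal and an adverse event as separate reasons for leaving, so a patient who stops because of an event is not necessarily caught by 4.5. Section 8.9 says "If the complication cannot be resolved, the subject will be discontinued from the study as described in Section 4.6". Patients discontinued by the investigator keep their data unless they also withdraw consent in writing. The protocol does not say how often each route would be taken. The study is descriptive, and no decision threshold depends on the count.

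The third reply is that the safety denominator belongs in the statistical analysis plan. Its full definition may well sit there. But if 4.5 is rewritten to keep events and is silent on the denominator, the same patients could still be handled in two ways, so one sentence in the same place is justified.

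A last point is that retaining data depends on what patients were told. That is correct. The consent form is not available here, and the fix has to respect it.

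**Conclusion.** The concern holds. Section 4.5 bars previously collected data after withdrawal of consent with no safety exception, section 10.1 promises analysis of all DISCSS-associated events, and nothing reconciles them. Confidence in this reading is high.

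The consequence is conditional. It arises only if a patient with a DISCSS-phase event later withdraws consent, and the protocol gives no basis for estimating how often that would happen. Under the assumed counts above, one such patient can take the serious event rate from 3.3% to 0%, or an adverse event rate from 10.0% to 6.9% or 6.7%. This should be fixed because it affects a primary endpoint and is cheap to correct. It does not call the design as a whole into question.

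**What to change.** Replace the last sentence of section 4.5 with wording such as:

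> If a patient withdraws consent, data collected up to the withdrawal of consent, at minimum all adverse events and DISCSS exposure, are retained and analyzed. Every patient connected to DISCSS stays in the denominator of the adverse event and serious adverse event rates.

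Then:

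- Change the exception in the first sentence of 4.5 to match, and use one trigger (written or not) in both sentences.
- State whether data gathered at or after withdrawal of consent, as foreseen in sections 4.3, 6.8 and 10.3, may be used.
- Consider keeping pain scores collected before withdrawal on the same terms. This is sensible, but section 10.1 does not require it.
- Align the consent form (Appendix I) and apply the new rule to patients who consent under the revised form. For patients who have already consented, follow the form they signed and report how many DISCSS-connected patients were left out for this reason.

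The cost is a short protocol amendment and a consent-form revision, both needing IRB/EC approval under section 13.1. The downsides are that event rates may look slightly less favourable and that patients may fall under two data rules according to the form they signed.
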